Metrics as reported by IC/ASA sites will be described (Section 7). Metrics will include consent rate, participant show rate, rate of notifications from HIV care providers and participants, participant return visit rate, reach (proportion of eligible individuals that participate in receiving injections at the IC/ASA), adoption (proportion of clinics contacted by the IC/ASA that initiate referrals for the injections), and fidelity (proportion of injections occurring within target window from target date). Metrics will be described for each site and aggregated across sites. Tables will display the rate, numerator and denominator used to calculate the rate, and the CI of the estimate.

A feasibility composite score will be derived from the following data: 1) FIM score; 2) consent rate; 3) show rate; 4) participant notification (appointment level); 5) HIV care provider notification (appointment level); and 6) return rate. The mean for each component of the composite score will be calculated across all data collections for that score and each component mean will then be multiplied by 100. The mean of these scores will then be calculated, producing a composite score where each component receives equal weight and the scale range is 0 - 100. The univariate distribution of feasibility composite score will be tabulated. The distributional characteristic table will include the mean and SD of the distribution, median, first and third quartiles, and 95% Cis using clinics as the unit of observation. Cronbach's alpha coefficient will be calculated to assess if the items consistently measure feasibility of implementation as a scale.

6 References

- 2. Cella D. Manual of the Functional Assessment of Chronic Illness Therapy (FACIT) Measurement System—Version 4. Evanston, IL: Center on Outcomes, Research & Education (CORE), Evanston Northwestern Healthcare and Northwestern University; 1997.

7 Table Shells: Baseline, Month 3, Month 8, and Change

Table 1.1.1. IC/ASA Staff Roles, Attitudes, and Anticipated Procedures in Implementing CABENUVA via IC/ASAs, Baseline (N=XX)

Question	Number of Participants at Baseline	Response	n (%)
		Front Desk Staff	n (%)
		Nurse Manager	n (%)
	XX	Clinic Nurse	n (%)
		Physician	n (%)
1.What is your role at the infusion center? ^{1,2}		Nurse Practitioner	n (%)

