Show Rate: Proportion of scheduled injection appointments that are not missed ^{2,3}				
Numerator: Number of scheduled injection appointments that result in shows	XX	XX	XX	(XX% -XX%)
Denominator: Number of confirmed scheduled injection appointments for participants				
Participant Notification – Appointment level: Proportion of missed appointments in which the infusion center contacts the participant ^{3,4}	XX	VV	VV	(VV0/ VV0/)
Numerator: Number of missed appointments for which the participant was contacted	XX	XX	XX	(XX% -XX%)
Denominator: Number of missed appointments				
HIV Care Provider Notification: Proportion of all appointments missed that are communicated to the HIV care provider ^{3,4}				
Numerator: Number of missed appointments that are communicated to the appropriate HIV care provider	XX	XX	XX	(XX% -XX%)
Denominator: Total number of missed appointments				
Return Rate at Visit N: Proportion of participants that completed any injection at Visit N after the completion of (N-1)th injection visit ⁵				
Numerator: Number of participants who returned to the IC/ASA and completed an injection at Visit N				
Denominator: Number of participants who completed an injection at the IC/ASA at the previous visit (N-1)	XX	XX	XX	(XX% -XX%)
— This definition is for any scheduled post-baseline visit. When N=1, the previous visit (N-1) is the baseline visit.				
Reach: Proportion of participants receiving injections at the infusion center/ASA as compared to the number of eligible participants through Month 8	VV	VV	VV	(VV0/ VV0/)
Numerator: Number of participants receiving their first injection Denominator: Number of eligible participants ⁶	XX	XX	XX	(XX% -XX%)

Item	Numerator (N)	Denominator (N)	Proportion (%)	95% Cl ¹
Adoption (Clinic level): Proportion of clinics contacted by the infusion center/ASA that initiate referrals for the injections Numerator: Number clinics initiation a referral Denominator: Number of clinical contacted to refer	XX	xx	XX	(XX% -XX%)
Adoption Provider level Numerator: Number providers who initiated a referral Denominator: Number of providers contacted by IC	XX	XX	xx	(XX% -XX%)
Fidelity: Proportion of injections occurring within target window from target date (+/-7 days of target date) ⁷ Numerator: Number injections in window Denominator: Number of injections ⁷	XX	XX	XX	(XX% -XX%)

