¹ Based on the normal approximation to the binomial distribution. Upper bound capped at 100% and lower bound capped at 0%.

² Injection appointments that result in shows were defined as an injection at visit N occurring during the target window. Baseline visits were excluded as no scheduled date was recorded. Participants who withdrew during the target window were counted as no shows.

³ Missed appointments were defined as any appointment for which no injection occurred among participants who reached the target window prior to study discontinuation.

⁴ No missed dose forms were completed, therefore participant and HIV care provider notification could not be determined.

⁵ Return rate was determined by counting the number of participants receiving an injection at visit N based on the number expected according to the number of participants at the previous visit.

⁶ Eligible participants included consented, declined study participation, not scheduled/lost to follow-up after referral. Eligible participants excluded those not receiving CABENUVA due to lack/change of insurance or cancellation by HCP, not enrolled due to site closure, not attending infusion center, and unknown and was prescribed CABENUVA every other month (before permitted in study) and <18 years of age.

 $^{^{7}}$ Target dates for injections were determined in accordance with the methodology implemented in the PLWHIV outputs. Abbreviations: CI = Confidence interval; HIV = human immunodeficiency virus; IC/ASA = infusion center/ alternate site of administration; IM = intramuscular; N/A = Not available; NE= Not estimable

A Phase 4, Open-label, Single-arm Study to Optimize Implementation of CABENUVA for the Treatment of HIV-1, for Administration in US Community-based Infusion Centers or Alternate Site of Administration

Table 7.2 IC/ASA Metric Reporting - Palmetto

Table 7.3 IC/ASA Metric Reporting - Medix

Table 7.4 IC/ASA Metric Reporting - Infusion Associates

Table 8. Distributional Characteristics of the Feasibility Composite Score

	Number of Clinics ¹	Missing	Mean	SD	Median (Q1, Q3)	Range (Min, Max)	95% Cl (Lower, Upper)	Cronbach's α²
Feasibility Composite Score ³	XX	XX	XX.X	XX	XX (X.X, X.X)	(X.X, X.X)	(X.X,X.X)	X.XX
FIM Score ⁴	XX	XX	XX.X	XX	XX (X.X, X.X)	(X.X, X.X)	(X.X,X.X)	X.XX
Consent Rate	XX	XX	XX.X	XX	XX (X.X, X.X)	(X.X, X.X)	(X.X,X.X)	X.XX
Show Rate	XX	XX	XX.X	XX	XX (X.X, X.X)	(X.X, X.X)	(X.X,X.X)	X.XX
Return Rate	XX	XX	XX.X	XX	XX (X.X, X.X)	(X.X, X.X)	(X.X,X.X)	X.XX

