Feasibility composite score includes FIM score, consent rate, show rate, participant notification appointment level, HIV care provider notification, and return rate across the entire study period within each clinic.

Participants are assigned to clinics based on the initial referral.

Participants are assigned to clinics based on the initial referral.

Abbreviations: CI = Confidence interval; FIM = Feasibility of Intervention Measure; SD = Standard deviation

¹ Includes only clinics consenting one or more participants.

 $^{^2}$ Standardized Cronbach's α . For components, Cronbach's alpha if item deleted is presented.

³ Feasibility composite score includes FIM score, consent rate, show rate, and return rate across the entire study period within each clinic. Participant notification appointment level, and HIV care provider notification were excluded as no missed dose forms were completed.

⁴ Based on proportion of PLWHIV endorsing all FIM items at a level of 4 or 5 at any timepoint.

A Phase 4, Open-label, Single-arm Study to Optimize Implementation of CABENUVA for the Treatment of HIV-1, for Administration in US Community-based Infusion Centers or Alternate Site of Administration

Table 9. Implementation Science-Related Protocol Deviations, N=XX

Protocol Deviation	IS-related Protocol Deviations For IC/ASA Staff (N= XX)	
	n(%)	
Total Sample IS-related Protocol Deviations	xx (xx.x)	
Questionnaire missing data	xx (xx.x)	
Questionnaire completed but not required	xx (xx.x)	
Questionnaire completed out of window (early)	xx (xx.x)	
Questionnaire completed out of window (late)	xx (xx.x)	
Duplicate questionnaire completed	xx (xx.x)	
Placeholder, other possible deviation	xx (xx.x)	

Abbreviations: IC/ASA = infusion center/ alternate site of administration

[figure not shown]
Note: Numerators equal the number of IC/ASA staff experiencing respective deviation type, denominators equal the number of IC/ASA staff in analytic dataset

 $^{^{1}}$ Deviations associated with incomplete IS questionnaires are for those initiated but not completed

8 Figures

[figure not shown]
Figure 1. Bar Chart Showing Mean IC/ASA Staff FIM and AIM Responses at Baseline, Month 3, and Month 8

Abbreviations: IC/ASA = Infusion center/ alternate site of administration; FIM = Feasibility of Intervention Measure; AIM = Acceptability of Intervention Measure; BL=Baseline; M3 = Month 3; M8 = Month 8 Error Bars = Standard error

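### IC/ASA Staff SAP Table 7.1 uses one capped normal-approximation interval for every rate: zero width at 0% or 100%, under-coverage at small denominators, and no allowance for repeated visits

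*SAP*

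**What the plan says.** Section 5 of the IC/ASA Staff SAP promises the site metrics for each site and in aggregate: "Tables will display the rate, numerator and denominator used to calculate the rate, and the CI of the estimate". It names no interval method. The method appears only in footnote 1 of Table 7.1, whose marker is on the 95% CI column header and so covers every row: "Based on the normal approximation to the binomial distribution. Upper bound capped at 100% and lower bound capped at 0" percent. The Staff SAP gives no exact or score alternative, no rule for 0% or 100%, and no adjustment for several records per person. It lists an abbreviation for not estimable but does not say when to use it.

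The rows differ in what they count.

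- Consent and reach count people. Adoption counts clinics or providers.
- Show rate counts appointments ("Number of scheduled injection appointments that result in shows"), after baseline only: "Baseline visits were excluded as no scheduled date was recorded".
- Fidelity counts injections: "Fidelity: Proportion of injections occurring within target window from target date (+/-7 days of target date").
- Return rate is defined visit by visit: "Proportion of participants that completed any injection at Visit N after the completion of (N-1)th injection visit".
- The two notification rows will have no estimate: "No missed dose forms were completed, therefore participant and HIV care provider notification could not be determined".

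The Clinical SAP takes a different line. Section 4.1.1 switches to exact methods where the normal approximation is unsuitable, and Section 4.7.4 uses Clopper-Pearson for the virologic proportions. The Staff SAP does not refer to either.

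**The concern.** These are rates that the sponsor hopes will be high, and some will rest on few records. That is where the normal-approximation interval performs worst. Capping the bounds at 0% and 100% hides the symptom without repairing the interval.

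Fidelity is a secondary endpoint in Protocol Section 3, and Section 6.3 promises a 95% CI for it. Table 7.1 is the only shell with a CI for that proportion: the adherence shells in the Participant SAP (Tables 8 and 9) have no CI column, and Table 8 counts participants rather than injections. A reader who wants to know how precisely fidelity was estimated has only this column to consult. If the interval is too narrow or collapses to a point, the implementation results look more certain than they are.

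**Working it through.** **No stated figure to reproduce.** The shells hold placeholders only, so the check is of the method.

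**Inputs.** At most 120 participants and about 35 sites (Protocol Section 6.1). Annex 1 schedules 8 injections for monthly dosing, and 5 or 4 for every-2-month dosing (starting or continuing). Dropping baseline leaves 7, 4 or 3 appointments for show rate. The documents give no within-person correlation (ICC), so ICC values of 0, 0.1 and 0.2 are assumptions. So are the true rates of 93% and 97%.

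**1. Boundary.** The half-width is 1.96 × √(p(1 − p)/n). At p = 0 or 1 this is zero for every n. For 20/20:

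- Footnote 1: 100%–100%.
- Wilson lower bound: n/(n + 1.96²) = 20/23.84 = 83.9%.
- Clopper-Pearson lower bound: 0.025^(1/20) = 83.2%.

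One miss in 20 gives 85.4% to 100% (capped) by footnote 1, against 76.4–99.1% by Wilson.

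**2. Coverage with independent records (ICC 0).** Coverage is the sum of the binomial probabilities of all counts whose interval contains the true rate. All-success samples, which give a zero-width interval, have probability p^n. The range n = 30 to 80 corresponds to an assumed unit of ten participants with three to eight visits each; 840 is 120 × 7.

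| n | Coverage, 93% | Coverage, 97% | Zero width, 93% | Zero width, 97% |
|---|---|---|---|---|
| 30 | 88.3% | 59.7% | 11.3% | 40.1% |
| 40 | 93.9% | 70.3% | 5.5% | 29.6% |
| 50 | 86.6% | 78.1% | 2.7% | 21.8% |
| 70 | 86.7% | 88.0% | 0.6% | 11.9% |
| 80 | 91.5% | 91.0% | 0.3% | 8.7% |
| 840 | 94.8% | 93.2% | about 0 | about 0 |

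Plain Wilson covers 93.7–97.8% in the n = 30 to 80 cells.

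**3. Repeated visits.** With m visits per person the variance is multiplied by 1 + (m − 1) × ICC, and coverage is about 2Φ(1.96/√that factor) − 1. At m = 7 the factor is 1 + 6 × 0.1 = 1.6 (87.9%) or 1 + 6 × 0.2 = 2.2 (81.4%). Simulation agrees (beta-binomial, 120 participants, 93% rate, 20,000 runs per cell):

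| Metric | ICC 0 | ICC 0.1 | ICC 0.2 |
|---|---|---|---|
| Show rate, 7 visits | 94.6% | 87.3% | 80.8% |
| Show rate, 3 visits | 94.0% | 90.9% | 88.0% |
| Fidelity, 8 injections, baseline in window | 94.7% | 87.1% | 81.2% |
| Fidelity, 4 injections, baseline in window | 94.4% | 92.1% | 89.7% |

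If every no-show ends participation, coverage is 93.2–94.6%, so there is no material loss.

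**The case against.** **The low coverage figures are not for the table that carries the footnote.** This stands. Table 7.1 is the aggregate. A reader might infer from 59.7% that its intervals are generally that poor; the documents do not support that, because the figure needs 30 records and a 97% rate. The site-level shells, Tables 7.2–7.4, appear by title only, so use of footnote 1 there is an inference. Splitting 120 participants evenly over those three tables (an assumption, giving n = 120 to 280) yields 91.9–94.5% coverage at 93% and 86–92% at 97%, with zero width in at most 2.6% of samples.

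**The size of the clustering effect is unknown.** This stands. It is tempting to say that show rate and fidelity are materially overstated in precision, but no ICC is given. Several features could limit the effect. Protocol Section 4.3.2 removes some participants after a missed injection. The Participant SAP's Table 8 notes set missed injections to missing and, for participants starting directly on injections, make the baseline target the injection date itself. Nor are the step 2 coverage figures free of the ICC: they assume it is zero. Only the zero width at 0% and 100% holds whatever the ICC.

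**Return rate has no repeated visits.** This stands as the row is defined. The phrase "return rate across the entire study period within each clinic" might suggest pooling, but it belongs to the composite score in Table 8. The row is affected only if the sponsor pools visits into its single cell.

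**The reader sees the numerator and denominator and can recompute.** This is partly true. It mitigates the boundary problem, but counts alone do not let a reader allow for repeated visits.

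**The Clinical SAP already has an exact fallback.** It does, but nothing carries that rule into the Staff SAP, which states a different method outright.

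**Conclusion.** The boundary failure is certain and needs no assumption about correlation. Under-coverage at small denominators or rates near 100% is established for independent records. In the aggregate table it matters mainly when a rate is near 0% or 100% or a denominator is small. For show rate and fidelity the direction of error is also clear (too narrow under any positive within-person correlation), but its size depends on an ICC that the documents do not supply: about 95%, 87% and 81% coverage at assumed values of 0, 0.1 and 0.2 with seven visits.

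Notification rows drop out because they cannot be determined. No decision rule uses these intervals, and neither the primary endpoint nor any point estimate changes. This is a minor point, worth correcting because fidelity is a protocol secondary endpoint with a promised interval.

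**What to change.** Replace footnote 1 of Table 7.1 with text to this effect:

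*Wilson score 95% CI (or Clopper-Pearson, as in the Clinical SAP) for all rows. For show rate and fidelity in the aggregate table, and for return rate if pooled over visits, a cluster-robust 95% CI that allows for repeated visits per participant, clustering on clinic where the number of clinics permits. For 0% or 100% cells, or where clustering cannot be estimated, the Wilson or exact interval, labelled as assuming independent visits.*

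Also state whether the return-rate row is per visit or pooled, and whether the same footnote applies to Tables 7.2–7.4.

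Clustering on clinic is preferable where feasible because the centers do the scheduling and reminders (Protocol Section 4.3.3). Adjusting for participants alone may not be enough: in simulations with an assumed site-level ICC of 0.05 or 0.1, a participant-only adjustment covered about 88% or 84%.

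The cost is one footnote, minor programming and slightly wider intervals. Section 3 of the Staff SAP already allows modifications that are justified and noted in the final report.

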Appendix A. Missing Data

Table A1. Summary of Missing Data

Timepoint	ltem	Completed n(%)	Missing n(%)
	FIM Item 1	n (%)	n (%)
	FIM Item 2	n (%)	n (%)
	FIM Item 3	n (%)	n (%)
Baseline	FIM Item 4	n (%)	n (%)
N=XX	AIM Item 1	n (%)	n (%)
	AIM Item 2	n (%)	n (%)
	AIM Item 3	n (%)	n (%)
	AIM Item 4	n (%)	n (%)
	FIM Item 1	n (%)	n (%)
	FIM Item 2	n (%)	n (%)
	FIM Item 3	n (%)	n (%)
Month 3	FIM Item 4	n (%)	n (%)
N=XX	AIM Item 1	n (%)	n (%)
	AIM Item 2	n (%)	n (%)
	AIM Item 3	n (%)	n (%)
	AIM Item 4	n (%)	n (%)
	FIM Item 1	n (%)	n (%)
	FIM Item 2	n (%)	n (%)
	FIM Item 3	n (%)	n (%)
Month 8	FIM Item 4	n (%)	n (%)
N=XX	AIM Item 1	n (%)	n (%)
	AIM Item 2	n (%)	n (%)
	AIM Item 3	n (%)	n (%)
	AIM Item 4	n (%)	n (%)

Abbreviations: AIM = Acceptability of Intervention Measure; FIM = Feasibility of Intervention Measure

Table A1. Summary of Free-text Responses

A Phase 4, Open-label, Single-arm Study to Optimize Implementation of CABENUVA for the Treatment of HIV-1, for Administration in US Community-based Infusion Centers or Alternate Sites of Administration:

Statistical Analysis Plan: Participants Living with HIV for Implementation Science Questionnaires

EVA-30466 | March 4, 2024 | Version 4.0

Prepared F	or:	
PPD		, GSK
PPD	, PhD PPD	, Global Implementation Research, ViiV Healthcare
ViiV		
Prepared E	By:	
PPD	, PhD	
PPD	, PhD MPH	
PPD	, PhD MPH	
Project Co	ntact:	
PPD		

Statistical Analysis Plan (SAP) Signature Page

SAP Title:

A Phase 4, Open-label, Single-arm Study to Optimize Implementation of CABENUVA for the Treatment of HIV-1, for Administration in US Community-based Infusion Centers or Alternative Site of Administration. Statistical Analysis Plan: Participants Living with HIV for Implementation Science Questionnaires.

SAP Date and Version: March 4th, 2024; Version 4.0

This SAP with the title, number, and version indicated above has been reviewed and approved by the Evidera Principal Investigators and Project Managers.

PPD	
	 Date
	 Date
	 Date
	Date

Table of Contents

1	INTF	RODUCTION	1
2	STU	DY DESIGN	3
	2.1	Description of the PLWHIV Questionnaire and Schedule for Completion	4
		2.1.1 Feasibility of Intervention Measure	4
		2.1.2 Acceptability of Intervention Measure	4
		2.1.3 PLWHIV Additional Questionnaire	4

Table 7. Implementation Science-Related Protocol Deviations, N=XX	47
Table 8. CABENUVA Adherence, Safety Set	47
Table 9. CABENUVA Adherence: days from the target dosing date at each study visit, Safety Set	48
Table A1. Summary of Missing Data	54
Table A2 Summary of Free-text Responses	54

List of Figures

Figure 1.	Bar	Chart Showing Mean PLWHIV FIM and AIM Responses at Baseline, Month 3, and Month 8	.50
Figure 2.	Bar	Chart Showing Proportion of PLWHIV Responding "Agree" or Completely Agree" on All FIM Items at Baseline, Month 3, and Month 8	.51
Figure 3.	Bar	Chart Showing Proportion of PLWHIV Responding "Agree" or Completely Agree" on All AIM Items at Baseline, Month 3, and Month 8	.51
Figure 4.	Bar	Chart Showing Change in Proportion of PLWHIV Responding "Agree" or Completely Agree" on All FIM Items, Baseline to Month 3, Baseline to Month 8	.52
Figure 5.	Bar	Chart Showing Change in Proportion of PLWHIV Responding "Agree" or Completely Agree" on All AIM Items, Baseline to Month 3, Baseline to Month 8, and Month 3 to Month 8	53

List of Abbreviations

Abbreviation	Definition
AIM	Acceptability of Intervention Measure
ART	Antiretroviral therapy
ASA	Alternative site of administration
BL	Baseline
CI	Confidence interval
EDC	Electronic data capture
FDA	Food and Drug Administration
FIM	Feasibility of Intervention Measure
HIV	Human immunodeficiency virus
IC	Infusion center
IM	Intramuscular
M3	Month 3
M8	Month 8
OCR	Optical character recognition
PDF	Portable document format
PLWHIV	Participants living with human immunodeficiency virus
QAP	Qualitative analysis plan
SAP	Statistical analysis plan
SD	Standard deviation
SoA	Schedule of Activities

1 Introduction

CABENUVA is a two-drug, co-packaged product of cabotegravir plus rilpivirine, both administered as long-acting, intramuscular (IM) injections once-monthly or every two months; it is an approved treatment for human immunodeficiency virus (HIV). Clinical trial results have shown that CABENUVA administered once-monthly or every two months is non-inferior to daily oral treatment for HIV.

Long-acting injectable treatments require changes in how HIV care is delivered. People living with HIV must attend appointments for their injections once a month or every two months, rather than seeing their providers several times per year for a prescription refill and monitoring visits. This poses new healthcare delivery challenges, including a shift in resources to this alternative means of delivering and receiving treatment—thus requiring the expansion of alternative injection facilities to include infusion centers (ICs) or alternate sites of administration (ASAs). This has the potential to impact workload capacity for these facilities, though it also has the potential to positively impact treatment engagement and retention for people living with HIV.

ICs/ASAs are an appealing option that can ease the burden of additional appointments, administrative work, and drug ordering in HIV specialty clinics, as well as provide people living with HIV with greater flexibility in where they receive their monthly or every two months injections. In this study, the intervention itself is the process of using an IC/ASA as the location to receive the CABENUVA IM injections. Specifically, the acceptability and feasibility of injection delivery at ICs/ASAs will be assessed from the perspectives of the participants living with HIV (PLWHIV), HIV care providers/clinical staff, and IC/ASA staff.

This statistical analysis plan (SAP) describes analyses for the acceptability and feasibility of an IC/ASA to deliver CABENUVA IM injections, as reported by study PLWHIV. It also encompasses a tailored questionnaire that asks PLWHIV about their experiences regarding their medication regimen, as well as their overall health, education, and employment status.

This is one of four SAPs for the following protocol: *Phase 4, open-label, single arm study to optimize implementation of CABENUVA for the treatment of HIV-1, for administration in US community-based infusion centers or alternate sites of administration.* The three additional SAPs are:

- (1) an additional SAP for clinical characteristics/analyses for PLWHIV, A Phase 4, open-label, single arm study to optimize implementation of CABENUVA for the treatment of HIV-1, for administration in US community-based infusion centers or alternate sites of administration: Statistical Analysis Plan for Clinical Analyses,
- (2) analyses for HIV care providers and Expert Panel, A Phase 4, open-label, single arm study to optimize implementation of CABENUVA for the treatment of HIV-1, for administration in US community-based infusion centers or alternate sites of administration, Statistical Analysis Plan: HIV Care Providers and key personal who are involved in the patients' care (Clinical Staff) & Expert Panel; and

(3) analyses for IC/ASA staff, A Phase 4, open-label, single arm study to optimize implementation of CABENUVA for the treatment of HIV-1, for administration in US community-based infusion centers or alternate sites of administration, Statistical Analysis Plan: Infusion Center Staff.

This SAP will describe the planned analyses for the primary and secondary quantitative objectives related to implementation science for PLWHIV as outlined in Table A. Additionally, this plan will not incorporate the planned qualitative interview analyses at the end of study. These analyses are detailed in the qualitative analysis plan (QAP) (currently under development).

Table A. Objectives and Endpoints for Participants

Objectives	Endpoints		
Primary			
To evaluate feasibility of CABENUVA administration at infusion centers or alternate sites of administration from participants	Proportion of participants that agree or completely agree (a score of 4 or higher) across all items on the FIM at Month 8		
Secondary			
To evaluate feasibility of CABENUVA	Proportion of participants that agree or completely agree (a score of 4 or higher) across all items on the FIM at Month 1, Month 3		
administration at infusion centers or	Change over time in the FIM at Month 3 and Month 8 with participants		
alternate sites of administration from participants	Summary of other quantitative questionnaires assessed with participants at Month 1, Month 3, and Month 8		
	Qualitative interviews assessed at Month 8 with participants (QAP)		
To evaluate feasibility of the process	Summary of composite score of the feasibility process indications through Month 8		
of administering CABENUVA at the infusion center/ ASA	Change over time through Month 8 in the composite score and each item of composite score.		
To evaluate acceptability of	Proportion of participants that agree or completely agree (a score of 4 or higher) across all items on the AIM at Month 1, Month 3 and Month 8		
CABENUVA administration at infusion	Change of participants over time in the AIM at Month 3 and Month 8		
centers or alternate sites of administration from participants	Summary of other quantitative questionnaires assessed at Month 1, Month 3, and Month 8 with participants		
	Qualitative interviews assessed at Month 8 with participants (QAP)		
To evaluate perceptions, facilitators,	Summary of participant other quantitative questionnaires at Month 1, Month 3 and Month 8 $$		
and barriers/concerns by participants	Qualitative interviews assessed at Month 8 with participants (QAP)		
To assess the preference of participants on the location to receive	Summary of preference on the location to receive CABENUVA at Month 1, Month 3, and Month 8 assessed by participant other quantitative questionnaires		
CABENUVA	Qualitative interviews assessed at Month 8 with participants (QAP)		
To assess the advantages to receive or refer participants to receive	Summary of advantages of receiving CABENUVA at IC/ASA at Month 1, Month 3, and Month 8 assessed by participant other quantitative questionnaires		
CABENUVA at the infusion center or alternate site of administration from participants	Qualitative interviews assessed at Month 8 with participants (QAP)		
To assess the disadvantages about	Summary of disadvantages of receiving CABENUVA at ICs/ASAs from participant other quantitative questionnaires at Month 1, Month 3, and Month 8		
receiving CABENUVA at the infusion	Qualitative interviews assessed at Month 8 with participants (QAP)		

Objectives	Endpoints	
center or alternate site of administration from participants		
To evaluate the acceptability of receiving and referring participants	Summary of acceptability of the process of receiving injections at ICs/ASAs from participant other quantitative questionnaires at Month 1, Month 3 and Month 8	
for CABENUVA injections at infusion centers or alternate sites of administration from participants	Qualitative interviews assessed at Month 8 with participants (QAP)	
To evaluate overall opinion of receiving and administering the injection at an infusion center or	Summary of overall opinion of receiving CABENUVA at an infusion center or alternate site of administration by participant other quantitative questionnaires at Month 1, Month 3, and Month 8.	
alternate site of administration by participants	Qualitative interviews at Month 8 with participants (QAP)	

Abbreviations: AIM = Acceptability of Intervention Measure; ASA=Alternative Site of Administration; FIM = Feasibility of Intervention Measure; IC = infusion center; QAP = Qualitative Analysis Plan

2 Study Design

This is a Phase 4, single-arm, open-label, multi-center study examining the administration of CABENUVA IM in ICs/ASAs in the United States. This study is being conducted following Food and Drug Administration (FDA) approval and commercial availability of CABENUVA. Eligible and consenting PLWHIV will be followed for eight months to evaluate an implementation blueprint for IM administration of CABENUVA for HIV-1 treatment at ICs/ASAs. The total duration for study PLWHIV is approximately eight months from the time of enrollment and receipt of the first administration of CABENUVA IM injections at the IC/ASA.

Relevant to this SAP, up to 120 PLWHIV who have been prescribed CABENUVA by their HIV care provider will be asked to complete questionnaires per the Schedule of Activities (SoA; see ANNEX 1 in protocol), as follows:

- Baseline/Month 1 questionnaires should be completed prior to receiving the first CABENUVA injections
- Baseline/Month 1 for each PLWHIV is defined as the date when a PLWHIV signs the informed consent form and completes Baseline/Month 1 protocol procedures prior to receiving the first CABENUVA injections at the IC/ASA
- Months 3 and 8 will be anchored off of each PLWHIV Baseline/Month 1 visit, so it will reflect the Months on study, regardless of what dose they are on and regardless of whether they have missed any injections and received oral bridging.

PLWHIV questionnaires consist of the Feasibility of Intervention Measure (FIM) and the Acceptability of Intervention Measure (AIM), as well as a tailored questionnaire.

